8.1.16 Safety evaluation method

(1) Incidence of anastomotic stoma dehiscence

Justification for selection: When stapler is used for intestinal anastomosis, it is necessary to select appropriate reload. Dehiscence of the anastomotic stoma may increase the risk to the subject. Therefore, the "incidence of anastomotic stoma dehiscence" is selected as one of the safety indicators of the product under evaluation. At the same time, with reference to the *Guidelines for Technical Review of Endoscopic Stapler Registration* issued by NMPA (original CFDA) on March 13, 2017, the "incidence of anastomotic stoma dehiscence" is selected as a safety evaluation indicator for such products.

Evaluation time: During the surgery.

Evaluation method: Anastomotic stoma dehiscence due to "staple popping" during surgery is recorded.

Formula: Incidence rate of anastomotic stoma dehiscence = number of eligible subjects in each group/total number of subjects in the group \times 100%

(2) Incidence of anastomotic stoma bleeding

Justification for Selection: Anastomotic stoma bleeding is a common complication in gastrointestinal anastomosis procedures, which will increase the risk to subjects. Therefore, "the incidence of anastomotic stoma bleeding" is selected as one of the indicators to evaluate the product safety. Meanwhile, with reference to the *Guidelines for Technical Review of Endoscopic Stapler Registration* issued by NMPA (original CFDA) on March 13, 2017, the "incidence rate of anastomotic stoma bleeding" is selected as a safety evaluation indicator for such products.

Evaluation time: from the end of surgery to the end of follow-up.

Evaluation method: Alimentary tract bleeding occurs after operation, and is confirmed as the anastomotic stoma source by observing digestive cavity decompression tube and intraperitoneal drainage tube, endoscope and angiography. If the source is not identified, it is then called gastrointestinal bleeding.

Formula: Incidence rate of anastomotic stoma bleeding = number of eligible subjects in each group/total number of subjects in the group \times 100%

(3) Incidence of anastomotic leakage

Justification for selection: Anastomotic leakage is a common complication of gastrointestinal anastomosis, which will increase the risk to subjects. Therefore, the "incidence of anastomotic leakage" is selected as one of the safety indicators for product evaluation. At the same time, with reference to the *Guidelines for*

Technical Review of Endoscopic Stapler Registration issued by China Food and Drug Administration on March 13, 2017, the "incidence of anastomotic leakage" is selected as a safety evaluation indicator for such products.

Evaluation time: From the end of surgery to the end of follow-up.

Evaluation method: Patients with at least one of the following items are considered as anastomotic leakage: A. imaging examination, such as gastrointestinal radiography, confirms anastomotic leakage; B. fecal substances appearing in the abdominal drainage tube or incision, in which other sources of intestinal tract can be excluded; C. reoperation exploration confirms anastomotic leakage; D. abdominopelvic abscess beside the anastomosis. Anastomotic leakage is divided into 3 grades according to the severity: Grade A: no special treatment is required; Grade B: active treatment is required, but no reoperation is required; Grade C: reoperation is required.

Formula: Incidence of anastomotic leakage = eligible subjects in each group/total number of subjects in this group \times 100%

Precautions: Necessary records should be kept for the treatment of anastomotic leakage.

(4) Incidence of anastomotic stricture

Justification for Selection: Anastomotic stricture is a common complication of gastrointestinal anastomosis, which will increase risks to subjects. Therefore, "the incidence of anastomotic stricture" is selected as one of the indicators to evaluate the product safety.

Evaluation time: From the end of surgery to the end of follow-up.

Evaluation method: The clinician judges whether the subject has an anastomotic stricture based on the symptoms, signs, endoscopy, angiography, etc.

Formula: Incidence rate of anastomotic stricture = eligible subjects in each group/total number of subjects in the group \times 100%

(5) Incidence of anastomotic stricture infection

Justification for Selection: Anastomotic stricture infection is a common complication of gastrointestinal anastomosis, which will increase risks to subjects. Therefore, "the incidence of anastomotic stricture infection" is selected as one of the indicators to evaluate the product safety.

Evaluation time: from the end of surgery to the end of follow-up.

Evaluation method: The clinician judges whether the subject has a staple line infection based on the symptoms, signs, endoscopy, angiography, etc.

Formula: Incidence rate of anastomotic stricture infection = eligible subjects in each group/total number of subjects in the group \times 100%

(6) Incidence of SAE (serious adverse event)

Evaluation time: During the whole clinical trial process.

Evaluation method: Serious adverse event refers to an event occurs in the process of clinical trials, which results in death or serious deterioration of health, including fatal disease or injury, permanent damage to the body structure or function, requiring hospitalization or prolonging the hospitalization, requiring medical or surgical intervention to avoid the permanent damage to the body structure or function; results in fetal distress, fetal death or congenital abnormality, congenital defect, etc.

Formula: SAE incidence = number of subjects with SAE in this group/number of all subjects in this group \times 100%.

Precautions: The adverse events related to the anastomotic stoma during clinical trial shall be considered as serious adverse events. Since "anastomotic stoma repair" may be associated with "anastomotic stoma dehiscence", the "anastomotic stoma repair "is not repeatedly considered a serious adverse event.

(7) Incidence of AE (adverse event)

Evaluation time: During the whole clinical trial process.

Formula: Incidence of adverse events = number of subjects with adverse events in this group/number of all subjects in this group \times 100%.

Definition: An adverse event is any untoward medical occurrence in a clinical investigation, whether or not related to the device. It is necessary to analyze the postoperative vital signs and laboratory tests (blood routine, biochemical indicators, etc.).

(8) Incidence of device defects

Measurement time: During the whole process of clinical trial.

Calculation formula: Incidence of device defect = number of device defects/total number of devices × 100%.

Precautions: A test device defect that occurs during the course of a clinical trial. "Staple pop" due to human factors (e.g., incorrect reload selection) is not a defect of the device.

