8.2.6 Device using specification

According to the results of random allocation, the investigators apply the study medical device to the subjects who enter the test group, and the control medical device to the subjects who enter the control group. If a subject requires the use of a circular stapler during the trial, the brand and model of the circular stapler shall be recorded.

⁹ Only the conditions related to the use of test product and control product are recorded here. However, during the trial, subjects may use circular stapler or other staplers. If adverse events related to the stapler also occur, the occurrence shall be truthfully recorded in the adverse events.

¹⁰ It is necessary to use gas injection method for inspection. If relevant examination is not required, the CRF should be completed as "Not Applicable".

¹¹ If yes, please specify the reason and whether it is related to the stapler.

¹² The model and amount used in the clinical trial shall be truthfully recorded. Meanwhile, whether the subject uses the brand and model of circular stapler shall also be collected.

¹³ Investigators faithfully record whether each reload is used laparoscopically or laparotomically.

¹⁴ The tissues cut and anastomosed by each cartridge, such as stomach, duodenum, jejunum, ileum, appendix, ascending colon, transverse colon, descending colon, sigmoid colon and rectum, etc. are recorded.

¹⁵ If corresponding symptoms occur, the reasons for confirming the event should also be briefly described, so as to facilitate the review. In addition, generally anastomotic bleeding is judged by the presence or absence of persistent fresh bleeding from the gastric tube, and the diagnosis is confirmed by gastroscopy or second surgical exploration.

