9.2 Sample Size Calculation

9.2.1 Total sample size

164 subjects are planned to be enrolled in this clinical trial. The sample size determination process is as follows:

This clinical study is a parallel positive control clinical validation design. The "anastomosis success rate" is adopted as the basis for sample size estimation. Based on literature review [3-11], the success rate of anastomosis is up to 100% when the similar devices are used for total laparoscopic distal gastrectomy for gastric cancer. According to relevant literatures and considering clinical practice, when such products are used for anastomosis from esophageal site to gastrointestinal site, the "success rate of anastomosis" can reach 97%. Therefore, the "anastomosis success rate" of this clinical trial is determined to be 97% with a clinical non-inferiority margin of 10%. The parameters are set as follows: $\alpha = 0.025$ (one-sided), $\beta = 0.2$, $\delta = 10\%$, and the ratio of test control group is 1:1. The estimation formula of sample size for non-inferiority clinical validation is adopted, and the sample size required in each group is at least 65 cases. The calculation formula [12] and correction formula [13] are as follows:

$$\begin{split} n_{A} &= \frac{(\pi_{A}(1-\pi_{A}) + \pi_{B}(1-\pi_{B}))(Z_{1-\beta} + Z_{1-\alpha})^{2}}{((\pi_{A} - \pi_{B}) - d)^{2}} \\ n_{B} &= \frac{n_{3} \left\{ 1 + \left[1 + 4/(\delta n_{A}) \right]^{\frac{1}{2}} \right\}^{2}}{4} \end{split}$$

Considering that the number of subjects who may drop out or be lost to follow-up during clinical validation is about 20%, the sample size of each group is expanded to 82 cases, and the total sample size required for the two groups is 164 cases.

9.2.2 Number of cases for clinical trial of each disease and reasons for determination

The investigational product is mainly used for the cutting and anastomosis of gastrointestinal tissues, other diseases therefore are not involved in this clinical trial.

9.2.3 Minimum and maximum number of subjects in each clinical trial institution and reason

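### The leakage definition has no drain or incision criterion for non-faecal content, although gastric, duodenal and jejunal anastomoses are in scope

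*Combined protocol and SAP*

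**What the plan says.** Section 8.1.16(3) sets the rule: "Patients with at least one of the following items are considered as anastomotic leakage". The four items are:

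- A: a leak shown on imaging, with contrast radiography given as the example
- B, the only item on drain or wound output: "fecal substances appearing in the abdominal drainage tube or incision, in which other sources of intestinal tract can be excluded"
- C: a leak found when the patient is operated on again
- D: an abscess in the abdomen or pelvis next to the anastomosis

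The same paragraph grades leaks from A to C. Grade B is a leak that is actively treated without reoperation.

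Footnote 14 (attached to 8.2.5.5(3)) asks for the tissue stapled by each cartridge, "such as stomach, duodenum, jejunum, ileum, appendix, ascending colon, transverse colon, descending colon, sigmoid colon and rectum". Section 9.2.1 draws its 100% success figure from "total laparoscopic distal gastrectomy for gastric cancer".

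On detection:

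- Footnote 8 (8.2.5.4) leaves angiography, upper gastrointestinal radiography and endoscopy to the investigator and allows an entry of not applicable.
- Section 8.2.7.3(3) lists a postoperative abdominal CT at Day 7 without footnote 8.
- Section 8.2.5.4(4) gives that CT one purpose: abdominal effusion and its amount.
- Footnote 2 to the flow chart in 8.2.1 makes postoperative imaging conditional on leakage or bleeding and on need.

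On recording, 8.2.5.5(4) has leakage as a yes/no follow-up item, and footnote 15 asks for a short reason for confirming the event. Section 9.5 tests safety indicators at 0.05 and reads p > 0.05 as no significant difference.

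**The concern.** B is the only one of the four items that rests on what comes out of a drain or wound, and its wording suits the lower bowel. A leak from a gastric, duodenal or jejunal staple line would be expected to drain gastric juice, bile, enteric fluid or food. That expectation is clinical reasoning and is not stated in the documents, but it is hard to dispute. Two subjects with the same course, both with leaking content in the drain and both treated without reoperation, can therefore be classified differently according to surgical site.

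Two things are at stake. If investigators apply the list as written, the leakage rate is undercounted in part of the trial population. If they use their own judgement instead, the count depends on investigators who know the allocation (8.1.3(4), 8.2.4). Undercounting in both arms shrinks the absolute difference. Because 9.5 reads a non-significant result as no significant difference, the loss works towards that conclusion.

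**Working it through.** **1. The plan's own figure.** The sample size rests on intraoperative anastomosis success, not on leakage. With 97% in both arms, margin 10%, one-sided alpha 0.025 and 80% power (9.2.1, 9.3):

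- Uncorrected: (2 × 0.97 × 0.03) × (1.960 + 0.842)² / 0.10² = 45.7, so 46.
- Corrected: (46/4) × [1 + √(1 + 4/(0.10 × 46))]² = 64.4, so 65.
- With 20% dropout: 65/0.80 = 81.25, so 82 per arm and 164 in total.

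The figure reproduces exactly, and the leakage definition does not enter it.

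**2. A literal reading of the rule.** Take a gastrojejunal leak on Day 5 with bile or food in the drain, treated without reoperation and without an abscess, with no imaging confirmation.

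| Item | Met? | Why |
|---|---|---|
| A | No | contrast study or endoscopy not done, or not confirming |
| B | No | output is not faecal |
| C | No | no reoperation |
| D | No | no abscess |

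The case fits the section's own Grade B description but satisfies none of the four entry items. After a colorectal anastomosis, the same course with faecal output meets B.

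**3. Do other provisions close the gap?**

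- *Clinician judgement.* Sections 8.1.16(4) and (5) let the clinician judge stricture and infection on symptoms, signs and investigations. Leakage has no such clause, so its list reads as closed.
- *Day 7 CT.* If routine, it reduces the number of subjects with no imaging at all. Its listed reading is effusion, however, and flow-chart footnote 2 makes imaging conditional. The Day 30 visit in 8.2.7.4 lists no CT.
- *Missing-data rule.* Worst-case handling of missing safety data (9.7.2(7)) does not help, because an unmet criterion is a recorded no and not a missing value.

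**4. Size, as illustration only.** Uncounted leaks per arm = 82 × incidence × upper-gastrointestinal share × share of those leaks shown by output alone. Only the incidence of 4% to 15% is the protocol's (14.1.5(2)). The two shares, 50–100% and 10–50%, are assumed.

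| Incidence | Low | High |
|---|---|---|
| 4% | 0.04 × 0.5 × 0.1 = 0.2 points; × 82 = 0.16 subjects | 0.04 × 1 × 0.5 = 2.0 points; × 82 = 1.64 |
| 15% | 0.15 × 0.5 × 0.1 = 0.75 points; × 82 = 0.62 | 0.15 × 1 × 0.5 = 7.5 points; × 82 = 6.15 |

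Taking both shares as 25–75% instead gives 82 × 0.04 × 0.25 × 0.25 = 0.2 to 82 × 0.15 × 0.75 × 0.75 = 6.9. In either version the spread comes mostly from the assumptions.

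**5. Effect on the test.** This is the exact power of a two-sided 0.05 Fisher test with 82 per arm, for an assumed doubling of the leak rate and equal loss in both arms:

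| True rates | No leaks missed | 25% missed | 50% missed |
|---|---|---|---|
| 15% vs 30% | 57% | 41% | 26% |
| 4% vs 8% | 10% | 6% | 3% |

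At 15% vs 30% with a quarter missed, the recorded rates are 11.25% and 22.5%. The ratio is kept, and the difference falls from 15 to 11.25 points. Power is already poor with full capture, so the definition worsens a weak comparison and is not the cause of its weakness.

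**The case against.** The strongest reply is that the uncounted case is an exception. It needs a leak that is recognised and treated but never confirmed. Footnote 8 provides for contrast radiography and endoscopy in just that situation, item A is open to any imaging, and the Day 30 visit lists those studies again. This stands as a limit on frequency. It does not remove the gap, because the studies are optional.

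A reader might infer that every upper-gastrointestinal leak without imaging or reoperation is scored as no leak. The documents do not support that. An abscess beside the anastomosis counts in its own right, with no required route of detection. The form also carries an investigator's yes/no answer with reasons, and nothing says that a clinically judged leak must be recoded to no. What remains is that the answer is not tied to A–D, so such a leak may go either way.

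A reader might also take leakage to be the main safety endpoint. It is one entry in an unranked list, with no margin and no part in the non-inferiority decision in 9.5. Nor would the event disappear from safety reporting: 8.1.16(6) treats anastomosis-related adverse events as serious. It would be absent only from the leakage comparison.

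Finally, the wording is the same for both arms, randomisation is stratified by centre (8.2.3), and 9.7.1 allows for centre effects. Differing gastric and colorectal mixes between centres therefore do little harm to the between-arm comparison. That stands. The remaining harm is the lower recorded rate and the room for unblinded discretion.

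**Conclusion.** The concern holds in a limited form. The leakage definition offers no drain or incision criterion for gastric, bilious, enteric or food content, although gastric, duodenal and jejunal anastomoses are included. A leak shown only by such output meets no written criterion unless imaging, reoperation or an abscess confirms it. It is then either omitted from the leakage rate or counted at the discretion of an investigator who knows the allocation.

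The size of the undercount cannot be derived from the documents. The range of about 0.2 to 6 subjects per arm of 82 should not be read as an estimate. Its upper end needs all subjects to have upper-gastrointestinal anastomoses, although 8.1.5.1 provides for rectal cases. It also needs half of their leaks to be shown by output alone, and the highest incidence quoted. The conclusion further rests on the clinical premise that upper-gastrointestinal leaks do not drain faecal matter. It concerns one safety indicator; the primary endpoint and the 164 subjects are untouched.

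**What to change.** Reword item B in 8.1.16(3) along these lines: *gastrointestinal content (gastric, bilious, enteric, food or faecal) in the abdominal drain or the incision, where a source other than the stapled anastomosis or staple line can be excluded*. Require the footnote 15 reason to state which of A–D was met. No separate site field is needed, since footnote 14 and 8.2.5.1(2) already record tissue and surgical site.

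Separately, reconcile 8.2.7.3(3), which lists the Day 7 abdominal CT without footnote 8, with flow-chart footnote 2 in 8.2.1, which makes postoperative imaging conditional.

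The cost is one reworded line and one more specific entry on the case report form. The new definition needs no added examination. The reported leak rate may be slightly higher in both arms.

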8.1.4 Measures for reducing and avoiding bias

- (1) Before the start of the study, the sponsor shall provide relevant training for the investigators participating in the study to ensure that the investigators fully understand the study process and are familiar with the operation of the study device; during the study, the investigators shall operate in strict accordance with the operating methods and procedures in the study protocol, and the clinical trial monitor shall do a good job in quality control and monitoring to ensure that the investigators operate and implement in strict accordance with the study protocol. The above measures shall be implemented throughout the implementation phase of the study to reduce errors or operational errors.
- (2) Subjects shall be screened in strict accordance with the clinical diagnostic criteria, as well as the inclusion and exclusion criteria of the trial protocol to reduce selection bias.
- (3) Total laparoscopic digestive tract reconstruction is difficult to operate, which should be carried out in centers with rich experience in laparoscopic surgery. In view of the learning curve of laparoscopic surgery, doctors can be more proficient based on at least 50 cases^[2]. The operating surgeon of laparoscopic surgery is recommended to be experienced in at least 100 cases of open surgery as the operator and 50 cases of laparoscopic surgery as the primary assistant.
- (4) When the clinical trial is completed, the data storage and collation shall be done well. When data problems are found, the data analyst shall check and confirm the data through the data clarification form to avoid recording errors.

8.1.5 Investigational medical device and control medical device or control diagnosis and treatment method

See the corresponding IFU for the diagnosis and treatment method with the investigational medical device and the reference medical device. In addition, subjects may use circular stapler or other types of staplers during the clinical trial. If these staplers are used, the investigators should truthfully record the model of these staplers and staple cartridge for reference.

When subjects experience adverse events related to the stapler, the investigators should truthfully judge the correlation between adverse events and the test device.

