9.7.1 Statistical method for data

Statistical analysis is performed using the SAS 9.1 software.

Statistical description on all data, including demographic data, baseline data, all efficacy indicators and all safety data shall be performed. Measurement data will be statistically described using mean, standard deviation, minimum, maximum, median, 25th percentile and 75th percentile; enumeration data will be statistically described using frequency and percentage.

The primary effectiveness evaluation indicator (anastomosis success rate) is evaluated by the confidence interval method.

The secondary evaluation indicators are evaluated by the difference test. Measurement data are compared using two independent samples t-test or Wilcoxon rank sum test. Enumeration data are compared using Pearson's X^2 test or Fisher's exact test.

The safety evaluation indicators are evaluated by the difference test. Enumeration data are compared using Pearson's X^2 test or Fisher's exact test. The adverse events and device defects occur in this trial shall be shown in list.

The stapler operational performance is evaluated by the difference test. Enumeration data are compared using Pearson's X^2 test or Fisher's exact test.

The central effect is considered in the analysis process. The general linear model is used for measurement data, and CMH or logistic regression is used for enumeration data.

9.7.2 Missing, unused, or incorrect data (including dropouts and withdrawals) and unreasonable data

All missing, unused or incorrect data (including dropouts and withdrawals) and unreasonable data will be discussed and finally determined by the investigators and biostatistician in the data review stage. The basic statistical principles for the processing of these data are as follows:

- (1) The details of each drop-out case shall be described, and the drop-out between the test group and the control group shall be compared using Pearson X^2 test or Fisher exact test;
- (2) Missing data at baseline shall not be estimated;
- (3) Missing values of main evaluation indicator (success rate of anastomosis) shall not be estimated;

Clinical Trial on Performance and Safety of Disposable Powered Articulating Endoscopic Linear Cutter Stapler in Gastrointestinal Tissue Cutting and Anastomosis

- (4) Missing values of secondary evaluation indicators shall not be estimated;
- (5) Missing values for operational performance evaluation shall not estimated;

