14.1.2 Adverse event grading

- (1) Mild: Symptoms inquired.
- (2) Medium: Symptoms that are actively described but can be tolerated.
- (3) Severe: Intolerable symptoms with objective manifestations.

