14.1.3 Reporting and handling of adverse events

All the adverse events and serious adverse events observed in the clinical trial should be clearly filled in the adverse event column of case report form. The duration of adverse event (i.e., the date of occurrence and disappearance of adverse event), severity, relationship with the clinical trial, and corresponding treatment and other handling measures should be recorded. Subjects occurring such event shall be followed up to end of the trial or the adverse event outcome.

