14.1.4 Correlation between adverse event and product

The correlation between all adverse events and study interventions must be judged by the investigators. The investigators then assessed based on temporal relationship and clinical experience. The followings are the evaluation criteria and judgment results of correlation:

- (1) The adverse event occurs within a reasonable time after the application of the device;
- 2) The adverse event can not be explained by other reasons;
- 3) The adverse event id relieved or disappeared after the the device is not applied;
- (4) The adverse event reappears after reapplication of the device.

Table 3. Correlation evaluation table

Standard	1)	2	3	4	
Results		_		_	
Definitely related	+	+	+	+	
Probably related	+	+	+	?	
Possibly related	+	-	?	?	
Unlikely related	-	-	?	?	
Unrelated	-	-	-	-	
"+" indicates conformity, "-" indicates non-conformity, "?" Indicates unable to judge					

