14.1.5 Handing protocol of adverse events that may occur in this clinical trial

- (1) Anastomotic bleeding: It is related to the factors of anastomotic leakage. The bleeding is generally the technical factor. The prevention is mainly to avoid the tension at the anastomotic stoma and the fat drop left at the cutting site.
- (2) Anastomotic leakage: The incidence of anastomotic leakage is reported to be 4% to 15% in the literature. It may be caused by the stapler, or related to the patient's condition or the doctor's operation;
- (3) Anastomotic stricture: It is one of the most common complications, mostly occurring after 1 month after surgery.
- (4) Major incisional bleeding: Drop in hemoglobin $\geq 20g/l$ resulting in ≥ 1 transfusion.
- (5) Minor incision bleeding: Bleeding that does not meet the criteria for "severe bleeding".
- (6) Incision site infection: Infection at the incision site due to improper nursing, resulting in prolonged incision healing time, prolonged suture removal time, or unplanned antibiotic therapy.
- (7) Delayed healing of incision: The incision in contact with suture has delayed healing time.
- (8) Anemia and hypoproteinemia: Symptoms caused by tumor deterioration in patients with gastric cancer;
- (9) Tumor recurrence or metastasis: Symptoms caused by further tumor deterioration in patients with gastric cancer;

(10) Gastrointestinal discomfort symptoms: Common symptoms of gastrointestinal diseases, such as nausea, belching, constipation, diarrhea, acid reflux, abdominal pain, etc.

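### Severity and relationship are recorded for every AE, but the only overall AE comparison counts any AE of any cause and grade, which dilutes a device effect in that indicator

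*Combined protocol and SAP*

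**What the plan says.** **What is collected.** Section 14.1.2 sets three severity grades, the top one being "Severe: Intolerable symptoms with objective manifestations". Section 14.1.3 requires for each AE that "severity, relationship with the clinical trial, and corresponding treatment and other handling measures should be recorded". Section 14.1.4 adds that "The correlation between all adverse events and study interventions must be judged by the investigators", on the five-level scale of Table 3. Section 8.1.5 says that, when stapler-related AEs occur, "the investigators should truthfully judge the correlation between adverse events and the test device".

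**What is compared.** Section 8.1.16(7) gives the AE indicator as "Incidence of adverse events = number of subjects with adverse events in this group/number of all subjects in this group". Its definition covers all causes: "An adverse event is any untoward medical occurrence in a clinical investigation, whether or not related to the device". Section 9.7.1 tests safety indicators by Pearson chi-square or Fisher, and Section 9.5 sets the level at 0.05 and reads p > 0.05 as no significant difference. The only other AE output in Section 9.7.1 is a listing: "The adverse events and device defects occur in this trial shall be shown in list".

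**What is foreseen.** The foreseeable AEs in Section 14.1.5 include "Common symptoms of gastrointestinal diseases, such as nausea, belching, constipation, diarrhea, acid reflux, abdominal pain". No expected AE rate is given for either arm.

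**The concern.** A difference between devices in AE incidence is one of the secondary objectives in Section 8.1.2. An indicator that pools all causes and grades mixes events the stapler could produce with events that follow from the disease, the operation or other treatment. A subject who already has an unrelated AE cannot move from no to yes because of the stapler, so the between-arm difference shrinks as the background rises.

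Several rules add to that background:

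- The AE observation period is the whole trial, and the flow chart in Section 8.2.1 marks AE recording at Visit 1, before any device is used.
- Footnote 9 in Section 8.2.5.5 sends events from circular and other staplers into the AE record. In rectal subjects of either arm who need a circular stapler, Section 8.1.5.1 specifies the same brand.
- Section 9.7.2(7) imputes missing safety values as the worst case. If applied to AE status, this adds AE subjects in both arms.

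At stake is a result reported as no significant difference when the comparison had little chance of showing one, with the data that could have separated the causes left in a listing.

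**Working it through.** **The plan's own figure.** The documents give no power or sample size for the AE comparison. The arm size comes from the primary endpoint and reproduces:

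- n = 2 × 0.97 × 0.03 × (0.842 + 1.960)² / 0.10² = 45.68.
- Correction: (45.68/4) × {1 + √(1 + 4/(0.10 × 45.68))}² = 64.1, rounded up to 65.
- Dropout: 65/0.80 = 81.25, rounded up to 82 per arm and 164 in total.

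**Inputs.**

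- From the documents: 82 per arm (Section 9.2.1) and α = 0.05 (Section 9.5), taken as two-sided.
- Assumed: a background AE rate q, equal in both arms, and device-related rates p that are independent of it.
- Two pairs of p are used. The first, 5% v 20%, is illustrative. The second, 4% v 15%, uses the two ends of the leakage range in Section 14.1.5(2), the only AE rate in the documents.

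**Formula.** Any-AE rate = 1 − (1 − q)(1 − p), so the between-arm difference is (1 − q) times the device-related difference. For q = 0.50 and 5% v 20%: 1 − 0.50 × 0.95 = 52.5% and 1 − 0.50 × 0.80 = 60.0%, so 15 points become 7.5.

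**Result** (exact Fisher power, 82 per arm):

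| Assumed background q | Any-AE rates from 5% v 20% | Power | Any-AE rates from 4% v 15% | Power |
|---|---|---|---|---|
| 0 (related AEs alone) | 5.0% v 20.0% | 80% | 4.0% v 15.0% | 61% |
| 20% | 24.0% v 36.0% | 33% | 23.2% v 32.0% | 19% |
| 50% | 52.5% v 60.0% | 12% | 52.0% v 57.5% | 8% |
| 80% | 81.0% v 84.0% | 5% | 80.8% v 83.0% | 4% |

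For 4% v 15%, a normal-approximation calculation puts the number per arm for 80% power at 111 undiluted, 404 at a 20% background, 1,285 at 50% and 4,807 at 80%. The trial is therefore short of 80% power for that contrast even without dilution.

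**The case against.** **Other safety comparisons exist.** Section 8.1.16 separately defines dehiscence, postoperative bleeding, leakage, stricture, infection, SAEs and device defects, and Section 8.1.15.2 compares stapler-caused conversion. AEs related to the anastomosis count as SAEs. Dehiscence and conversion already build in attribution to the stapler. A reader might infer from the table that the trial cannot show a device effect on safety. The documents do not support that: the dilution concerns one indicator, and most events a stapler would plausibly cause enter a more specific line. This part of the objection stands. It does not close the gap entirely. Dehiscence covers only intraoperative staple popping, bleeding of unidentified source is classed as gastrointestinal bleeding instead, and the SAE rate is itself all-cause. A non-serious stapler-related event outside the named categories is compared only within any AE.

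**Saturation is not shown.** A reader might also infer that nearly every subject will have an AE. No AE rate is given, and Section 14.1.5 calls the listed symptoms common in gastrointestinal disease, without saying how many subjects will have them. This stands too, but the point does not need saturation: a 20% background already cuts power by more than half.

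**Relatedness is a weak instrument here.** In Table 3, possibly related means plausible timing together with another available explanation, so that cut readmits background. If 10% of subjects in each arm had such an event, power for 5% v 20% would fall from 80% to 49%. The criteria on stopping and reapplying the device fit a single-use stapler poorly, and investigators know the allocation (Section 8.2.4). This is a good reason not to replace the any-cause comparison. It is not a reason to omit the breakdown.

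**The SAP is still to come.** Section 9.1 defers the detailed methods to a SAP finalised before database lock. That makes the change easy, but Section 9.8 treats analyses added outside that plan as exploratory.

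**Conclusion.** The point holds for the overall AE indicator. Severity grade and Table 3 relationship are to be recorded for all AEs, and no planned comparison uses either. Under the stated assumptions, Fisher power for a device effect falls from 80% to between 33% and 5% (5% v 20%), or from 61% to between 19% and 4% (4% v 15%), as the background rises from 20% to 80%. These sizes rest on assumed backgrounds, an assumed device effect and independence of the two; the direction rests only on the pooling. Other planned comparisons partly cover device effects, so this is a worthwhile improvement to safety reporting and not a failure of the safety assessment.

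**What to change.** In Sections 8.1.16(6)–(7) and 9.7.1, and in the SAP before database lock, pre-specify for each arm, counting each subject once:

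- incidence of AEs related to the study stapler;
- incidence of SAEs related to the study stapler;
- incidence of severe AEs.

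Give each a risk difference and 95% interval, so that a wide interval is not read as absence of a difference. Keep the any-AE and any-SAE comparisons as they are.

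State that relationship means relationship to the study stapler. Section 14.1.3 speaks of the clinical trial and Section 14.1.4 of study interventions, and other staplers may be used in the same subject. Show counts at every Table 3 level, so that the reader can see how far the result depends on the possibly related category.

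**Cost.** Some wording and a few table rows. Sections 14.1.3 and 14.1.4 already require severity and relationship to be recorded; the CRF is not among the documents, so check that its relationship field refers to the study stapler. The drawback is that relatedness is judged by unblinded investigators, so these rows are supportive and must be read beside the any-cause rows.
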